Cerebrovascular disease	Lee 1999, Kheterpal 2009, Botto 2014

Peripheral vascular disease	Botto 2014
Diabetes	Lee 1999 (Insulin-dependent), Botto 2014 (though not found to be predictive in Kheterpal 2009)
RCRI	Lee 1999
Hypertension	Kheterpal 2009 (hypertension requiring medication), Botto 2014, Ruetzler 2020 (4)
Kidney function (laboratory)	Lee 1999, Botto 2014 (though not found to be predictive in Kheterpal 2009)
BNP / NT-proBNP	Choi 2010 (13), Rodseth 2013 (14) and 2014 (15) metanalyses, Malhotra 2016 (16), Duceppe 2020 (17)
Anemia	Feng 2017 (18)
Heart rate	Abbott 2016 (>96) (19), Laitio 2004 (increased variability) (20), Devereaux 2011 (every increase by 10 from baseline) (21)
American Society of Anesthesiologist physical status	House 2016

Table 2. Intraoperative factors studied in literature associated with MINS and/or major myocardial complication and mortality

Variable	References
Type and risk of surgery (various definitions)	Lee 1999, Boersma 2005 (22), Davenport 2007 (23) Not found to be predictive in Kheterpal 2009 likely due to different definitions and study populations.
Emergency surgery	Detsky 1986 (24), Boersma 2005, Kheterpal 2009, Botto 2014, House 2016, Zhao 2017 (25), House 2016 Emergency surgery patients excluded in RCRI (Lee 1999)
Red blood cell (RBC) transfusion	Kheterpal 2009, Whitlock 2015 (26), Wu 2010 (27), Glance 2011 (28), Devereaux 2011

Hypotension (mmHg)	Wesselink 2018 (29), Sessler 2018 (30)
Tachycardia (beats)	House 2016 (>100 beats for >59 minutes), Abbott 2018 (>100)

Table 3. Postoperative factors studied in literature associated with MINS and/or major myocardial complication and mortality

Variable	References
Postoperative hypotension	van Lier 2018 (quartiles, 3 days postoperatively) (31), Sessler 2018 (<90mmHg, 4 days postoperatively) Liem 2020 (duration MAP <75, 24 hours postoperatively) (32)
Acute kidney injury	Zhao 2017
Vasopressor use 24 hours after surgery	Zhao 2017

Objectives

1. To develop and internally validate a model that uses the duration and degree of intraoperative and postoperative hypotension to predict the daily maximum troponin level from postoperative days zero to two, in a high risk population where troponin monitoring was ordered.

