2. To develop and internally validate a model that uses the duration and degree of intraoperative and postoperative hypotension to predict daily probability of MINS or death (binary outcome, according to the 2021 American Heart Association (AHA) definitions (6) from postoperative days zero to two.
3. To evaluate how different definitions of hypotension affect the primary and secondary models above, and analyze the intraoperative and postoperative hypotension separately to determine whether intraoperative or postoperative hypotension alone are sufficient for prediction.
4. To explore whether other intraoperative and postoperative vital sign information (heart rate, oxygen saturation, and end-tidal carbon dioxide derangements at various definitions) add predictive value to the primary and secondary models above.
5. To use machine learning methods to perform exploratory analysis to determine 1) optimal methods for imputation for time series data; 2) visualization of time series data in the setting of prediction; 3) development and internal validation of machine learning models to use the time series data to predict troponin levels; and 4) to determine how many hours earlier than a binary MINS diagnosis were vital signs able

to predict a MINS diagnosis (as determined by when in the time series prior to MINS diagnosis that the model achieved various thresholds of predicted probability).

Methods

This is a single-center, retrospective cohort study on the development and internal validation of a prediction model.

Population

This study will include patients aged 45 years and older undergoing inpatient noncardiac surgery, who had MINS protocol ordered for postoperative high sensitivity troponin monitoring based on the CCS guidelines (5) from January 2020 to June 2021 (estimated sample size of 750, event rate of ~75).

Patients will be excluded if they do not have intraoperative and postoperative vital signs, or any postoperative troponin measurements. Patients who underwent repeat surgery or were readmitted within the first 72 hours postoperatively will be excluded, since patients who are discharged and readmitted will not have vital measurements as outpatients. If a patient had multiple admissions where the MINS protocol was ordered, only the first inpatient admission will be included. Patients who had positive troponin on postoperative day 4 will be excluded, since vital signs are only included up to postoperative day 3 for consistency.

Data sources

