Following research ethics board approval, data will be extracted from Cerner Surginet Anesthesia (intraoperative electronic records) and Cerner PowerChart (preoperative and postoperative electronic records). The extracted data will consist of cohort characteristics (patient, anesthetic, surgical variables relevant to MINS (see Data Dictionary below), and patient vital signs with time stamps up to postoperative day 3. The time series time stamps will be transposed to have the start of surgery as 00:00, Jan 1, 2020. A manual chart review will also be performed to extract data not automatically retrieved from Cerner and Surginet (e.g. diagnoses of morbidities). We will extract relevant preoperative comorbidities, including RCRI and Charlson Comorbidity Index categories that are available to the Cerner team via CIHI with no date limit to obtain all preoperative comorbidities (please see Appendix). The Cerner, Surginet, and chart review data will then be linked by de-identified study ID and full surgery date.

Duration of data collection

Preoperative laboratory values are collected within 30 days before surgery. Preoperative vitals are collected within 24 hours before surgery. The total duration of subsequent data collection will be from the time of surgery up to postoperative day 3 (since the MINS protocol monitors for 3 days) or hospital discharge or death, whichever occurs first. Since 90% of MINS happen between postoperative days zero and two (4) and the frequency of monitoring would likely decrease by postoperative day 3, we will model troponin from postoperative day 0 to postoperative day 2 for the primary analysis to balance utility of the temporal model and prediction data quality.

Outcome

In the primary model, we will model high-sensitivity troponin (hsTnT) level as a continuous outcome, such that the model will remain useful if the troponin threshold definitions for MINS evolve.

In the secondary model, we will use the American Heart Association (AHA) definitions (6) for MINS, briefly:

1. Postoperative hsTnT 20 to <65 ng/L with an absolute increase of ≥ 5 ng/L amongst any postoperative troponins, or ≥ 65 ng/L, “attributable to a presumed ischemic mechanism (ie, supply-demand mismatch or atherothrombosis) in the absence of an overt precipitating nonischemic cause (eg, pulmonary embolism)”. The timestamp for laboratory diagnosis will be set at the time that the sample of elevated troponin was drawn.

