The Cerner, Surginet, and chart review data will then be linked by de-identified Cerner study ID. The time series time stamps will be shifted to have the start of surgery as 00:00, Jan 1, 2020, in order to standardize the times for longitudinal modeling. Data will then be processed for removal of vital sign artefacts per the Multicentre Perioperative Outcomes Group protocol (35). To generate a final blood pressure dataset, if noninvasive blood pressure and invasive blood pressure are available during the same minute, then the measurement that is 1) not marked as artefact and 2) has a higher systolic blood pressure will be taken. Data will also be processed for calculation of RCRI, determination of the timing of MINS diagnosis, truncation of vital sign time series to the appropriate time stamp (see below), and calculation of duration under threshold of the time series to create vital sign summary variables as described in Table 4 for each postoperative day (0-<24h, 24-<48, 48-<72, and <72-96h after surgery end time). A formal chart review will also be performed to extract data not automatically retrieved from Cerner and Surginet, and verify data quality of automatically extracted comorbidities.

For modeling troponin as a continuous outcome, the vital sign time series will be truncated at the last troponin measurement within 3 days of surgery. For modeling the binary MINS outcome definitions the data will be truncated at the time of troponin laboratory diagnosis of the outcome event, postoperative day 3 (since the MINS protocol monitors for 3 days) or hospital discharge or death, whichever occurs first. All time measurements will be standardized as above in relation to the surgery start time.

Predictive Modeling Approaches

Approach I. Analysis using conventional longitudinal modeling (primary objective)

Data visualization

The initial exploratory analysis of the vital signs and troponin data involves time series visualizations and summaries to explore any potential patterns present in the data that may be associated with troponin quantiles or MINS or myocardial injury diagnosis. Spaghetti plots of the longitudinal data will be created for the outcome and vital signs variables, with lines colour-coded by troponin quantiles or MINS or myocardial injury diagnosis. Other relevant visualizations (scatterplots, boxplots, etc.) examining the associations between the troponin outcome and the vital signs variables will also be created.

Primary Modeling

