The primary analysis will involve building a linear mixed effects model (with random intercepts) to predict the maximum daily troponin level between postoperative days 0 to 2 as the continuous outcome. The postoperative days 0, 1, and 2 accounts for approximately 40%, 40%, and 10% of MINS, respectively (4). Due to the limitations in retrospective data and the daily troponin monitoring, we will use day as a unit for time rather than hour to avoid overestimation of precision by readers.

For the primary and secondary models described in Objectives 1 and 2, an *a priori* list of predictors will be used: duration hypotension (summarized as a percentage of duration of MAP<75 mmHg in the duration of time modeled, e.g. postoperative day 1) age, sex, emergency surgery, RCRI, and postoperative GFR, as well as the postoperative day and the interaction between postoperative day and % duration MAP<75 mmHg as detailed below.

For longitudinal modeling, the vital signs data and troponin data will be aggregated to the day level, so that the model can predict at the daily temporal level. If there are multiple troponin measurements on the same day, the maximum will be taken. This aggregation of the data is necessary to account for the fact that the vital signs and troponin measurements are measured at irregular intervals (both across patients and data types), often due to the acting physician's response to the patient's condition. Additionally, due to this characteristic of the raw data, the vital signs predictors will be created such that they are standardized to be robust to the number of daily measurements performed (for example, by taking the percentage of day duration, NOT the total duration, of blood pressure below a specific threshold across all measurements during that day). A categorical time variable (representing the day of the measurement) will be included as a predictor within the model.

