Preoperative ACEI/ARB	Preoperative use (captopril, enalapril, ramipril, perindopril, lisinopril, candesartan, irbesartan, losartan, telmisartan, valsartan, sacubitril/valsartan) 1/0 Yes/No	Potential predictor Potential confounder Note that in order to obtain these variables and due to the limited analytic time from the Cerner team, all medications in the patient's medication administration record that is noted as completed were pulled
Postoperative Phenylephrine (>200mcg)	1/0 Yes/No	Potential predictor Potential confounder
Postoperative Ephedrine (>10mg)	1/0 Yes/No	Potential predictor Potential confounder

Postoperative Norepinephrine	1/0 Yes/No	Potential predictor Potential confounder
Postoperative Vasopressin	1/0 Yes/No	Potential predictor Potential confounder
Postoperative Epinephrine	1/0 Yes/No	Potential predictor Potential confounder
Postoperative Dobutamine	1/0 Yes/No	Potential predictor Potential confounder
Postoperative Milrinone	1/0 Yes/No	Potential predictor Potential confounder
In hospital mortality	1/0 Yes/No	Outcome Cohort characteristic
Start of surgery (time/date) [Enters OR]	Time/date	To define the start of the time series
End of surgery (time/date) [Leaves OR]	Time/date	To define the start of the postoperative time series
Length of OR	Duration in minutes	Potential predictor
PACU length of stay	Duration in minutes (if available, otherwise calculated based on the following two values)	Potential Predictor
Time of PACU admission	Time/date	For time stamps
Time of PACU discharge	Time/date	For time stamps
Time/date of hospital discharge	Time/date	To verify inclusion criteria
Readmission within 3 days of surgery	1/0 Yes/No	Patients who underwent repeat surgery or were readmitted within the first 72 hours postoperatively will be excluded.
Repeat surgery within 3	1/0	Patients who underwent

days of surgery	Yes/No	repeat surgery or were readmitted within the first 72 hours postoperatively will be excluded.
-----------------	--------	---

CIHI – Canadian Institute for Health Information, ICD-10 (International statistical classification of diseases and related problems) codes

References:

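### Excluding patients with repeat surgery or readmission within 72 h selects the cohort on events inside the day 0–2 prediction window, and the stated reason does not support it

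*Combined protocol and SAP*

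**What the plan says.** The rule is in the Population section: "Patients who underwent repeat surgery or were readmitted within the first 72 hours postoperatively will be excluded". The reason follows directly: "since patients who are discharged and readmitted will not have vital measurements as outpatients". The Data Dictionary repeats the rule beside the readmission and repeat-surgery variables, both yes/no flags for the 3 days after surgery. The whole patient is removed, not just the time after the event.

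The primary objective is to "predict the daily maximum troponin level from postoperative days zero to two" among high-risk patients with troponin monitoring ordered. The second objective covers the daily probability of MINS or death over the same days.

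For patients who stay in the cohort, three rules deal with shortened follow-up:

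- Duration of data collection ends collection at postoperative day 3 "or hospital discharge or death, whichever occurs first".
- Data processing says that for the binary outcome "the data will be truncated at the time of troponin laboratory diagnosis of the outcome event, postoperative day 3", discharge or death.
- Data processing says that for the continuous outcome "the vital sign time series will be truncated at the last troponin measurement within 3 days of surgery".

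Repeat surgery is not a stopping point in any of them. Under Primary Modeling, vital sign predictors are standardised "by taking the percentage of day duration, NOT the total duration".

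**The concern.** A prediction model should be developed on patients who can be recognised when the prediction is made. Here, whether a patient belongs to the cohort is settled only after 72 h, when the last predicted day is over. A clinician using a day 0 or day 1 prediction cannot tell whether the patient in front of them belongs to the population the model describes.

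The rule can also delete outcomes that were already complete. Only the first MINS event counts, and hemodynamic data stop there. For a patient with MINS on day 0 and a second operation on day 2, everything the binary model needs comes before the reoperation, yet patient and event are both dropped.

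Internal validation cannot expose this, because cross-validation, calibration and decision curves all run inside the selected cohort. The listed sensitivity analyses vary the cut before MINS diagnosis but never bring these patients back. The cohort description does not list the number excluded or their outcomes. The plan takes more care with early death, which it counts as an event to avoid bias even though it expects such deaths to be very rare.

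**Working it through.** **1. The windows coincide.** Data processing defines days 0, 1 and 2 as 0–<24, 24–<48 and 48–<72 h after surgery. The exclusion window is also 72 h.

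**2. The reason set against the patients it is meant to cover.**

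| Patient | Outpatient gap in vital signs? | Handling in the plan |
|---|---|---|
| Discharged before 72 h, not readmitted | Yes | Kept, stopped at discharge |
| Discharged and readmitted before 72 h | Yes | Removed entirely |
| Repeat surgery in the same stay | No | Removed entirely |

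The first two rows have the same data up to discharge and differ only in what happens later. The third row has no outpatient gap at all.

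**3. The plan's own figures.** Population gives an estimated 750 patients and about 75 events: 75/750 = 10.0%. The parameter limits follow: 750/15 = 50 patients per term, and 75/10 = 7.5, rounded to 8 variables (75/8 = 9.4 events per variable). The 750 and 75 are not derived, and the plan does not say whether they are before or after exclusions.

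**4. Size over an assumed range.** The documents give neither the excluded share f nor the event-risk ratio RR (excluded versus retained). I assume f = 1–5% and RR = 1–4.

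*If 750/75 are after exclusion:* patients added = 750/(1 − f) − 750; events added = patients added × 0.10 × RR; full-cohort rate = 0.10 × (1 − f + f × RR).

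| f | RR | Patients added | Events added | Full-cohort rate | Share of all events |
|---|---|---|---|---|---|
| 1% | 1 | 7.6 | 0.8 | 10.0% | 1.0% |
| 1% | 4 | 7.6 | 3.0 | 10.3% | 3.9% |
| 2% | 3 | 15.3 | 4.6 | 10.4% | 5.8% |
| 5% | 1 | 39.5 | 3.9 | 10.0% | 5.0% |
| 5% | 4 | 39.5 | 15.8 | 11.5% | 17.4% |

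The shift is 0 to 1.5 percentage points. If RR were below 1 the sign would reverse; at f = 5% the rate could fall no lower than 0.10 × 0.95 = 9.5%.

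*If 750/75 are before exclusion:* retained rate = 0.10/(1 − f + f × RR). At f = 5%, RR = 4 this is 0.10/1.15 = 8.7%. Events lost = 37.5 × 4 × 0.087 = 13.0, leaving 62.0, or 62.0/8 = 7.7 per variable. At f = 1%, RR = 1 about 74 events remain, or 9.3 per variable.

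**5. What truncation would recover.** The event counts above include every event in excluded patients. Stopping at discharge or reoperation returns only the events before that time, so the counts are upper bounds on the gain.

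**The case against.** The strongest defence is that a single-surgery cohort is a coherent choice. Time is anchored to one surgery start, the day bins to one surgery end, and urgency is defined for the index operation. A second operation brings a second intraoperative exposure that this structure cannot represent. That stands as a reason to stop follow-up at reoperation. It is not the reason the plan gives, and it does not require deleting the days before reoperation.

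Four stronger readings are tempting, and the documents do not support them:

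- *The existing truncation rule would already keep everyone.* It fits readmission only. A stop at repeat surgery would be new, and the dictionary holds only a yes/no flag for it.
- *Reoperated inpatients have continuous vital signs.* The plan says ward measurements may be less frequent. What can be said is that these patients are still in hospital, so the outpatient gap does not arise.
- *The exclusion is known to remove patients with more hypotension and more MINS.* This is clinically plausible, but Tables 1–3 list neither repeat surgery nor readmission. The nearest entries are transfusion and emergency surgery.
- *A definite share of the 75 events is lost.* Any such figure rests on assumed rates, equal risk cannot be ruled out, and the 75 may already be net of exclusions.

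The remedy is not free of bias either. If reoperation is prognostic, stopping there is informative. The day on which it falls would also give a troponin maximum over a partial day, possibly before that day's sample.

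**Conclusion.** The point holds as a design flaw of unknown size. Two things are plain in the text: eligibility depends on events within the prediction window, and the stated reason neither covers repeat surgery in the same stay nor justifies treating readmitted patients differently from others discharged early.

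A reader might infer that the model will underestimate risk, or that a material fraction of events is lost. Neither follows. With equal risk the event rate does not move at all; under the assumed 1–5% excluded and risk ratio 1–4 it moves by at most about 1.5 percentage points. The event rate is also only a partial measure: the documents allow no estimate of the effect on the hypotension coefficients or on calibration. The plan should be changed because the correction is cheap and nothing now planned would show whether the exclusion matters.

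**What to change.** - **Readmitted patients:** keep them and apply the existing stop at index discharge to both models. "Time/date of hospital discharge" is already extracted. State that troponins after index discharge are not used, because the continuous-outcome cut at the last troponin within 3 days does not itself name discharge.
- **Repeat-surgery patients:** keep them up to the start of the second operation, written in as a new stopping point. The time can come from the Surginet room-entry record or the planned chart review. Earlier days and earlier MINS events then count.
- **Reporting:** give the number affected, split by reason, with their troponin and MINS status, and show results with and without them. Also show results that drop the day cut by reoperation.
- **If the exclusion is retained:** give a reason that covers repeat surgery, restrict the target population explicitly, and still report the number excluded with their outcomes.

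The cost is revised eligibility and truncation wording and a few operation times to pull. The possibly informative stop and the partial-day maximum remain as limitations to declare.

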PE	Presence of pulmonary embolism within MINS window CIHI postoperative diagnoses: I26 1/0 Yes/No	MINS diagnosis criteria
Atrial fibrillation	Presence of atrial fibrillation within MINS window CIHI postoperative diagnoses: I48.x 1/0 Yes/No	MINS diagnosis criteria
Cardioversion	Cardioversion within 24 hours MINS 1/0 Yes/No	MINS diagnosis criteria
Sepsis	Presence of sepsis within MINS window CIHI postoperative diagnoses: R57.2 1/0 Yes/No	MINS diagnosis criteria
MINS	Based on MINS diagnostic criteria as described (primary outcome) 1/0 Yes/No	MINS diagnosis criteria
MIpost	Diagnosis of myocardial infarction postoperatively 1/0 Yes/No	Third Universal Definition or per cardiology note

PMI	Diagnosis of postoperative myocardial injury postoperatively 1/0 Yes/No	StEP criteria
Troponin	Preoperative and postoperative HS troponin values with time stamps Value in ng/L	MINS diagnosis criteria Time of MINS diagnosis Exclusion Criteria Patients who had positive troponin on postoperative day 4 will be excluded, since vital signs are only included up to postoperative day 3 for consistency.
Estimated blood loss	Intraoperative recorded blood loss Volume in mL	Potential predictor
Surgical Service	Vascular General Orthopedics ENT Gynecology Plastics Other	Potential predictor
High risk surgery	Suprainguinal vascular, intrathoracic, intraperitoneal 1/0 Yes/No	Potential predictor RCRI
Disposition postoperatively	Ward vs HAU vs ICU	Cohort Characteristic
HAU admission start time	Time stamp	Determine setting of vital measurement
HAU admission end time	Time stamp	Determine setting of vital measurement
ICU admission start time	Time stamp	Determine setting of vital measurement

ICU admission end time	Time stamp	Determine setting of vital measurement
Preoperative NT-proBNP	Value in ng/L	Potential predictor
Preoperative Hemoglobin	Value in g/L	Cohort characteristics Potential predictor
Preoperative GFR	Value in mL/min	Cohort characteristics Potential predictor
Preoperative beta blocker use	Preoperative use (metoprolol, bisoprolol, carvedilol, atenolol, propranolol, labetalol, nadolol) 1/0 Yes/No	Potential predictor Potential confounder Note that in order to obtain these variables and due to the limited analytic time from the Cerner team, all medications in the patient's medication administration record that is noted as completed were pulled

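### Excluding patients with a positive troponin on postoperative day 4 selects the cohort for the day 0–2 models on a future result those models do not need; the likely effect is small

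*Combined protocol and SAP*

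**What the plan says.** Methods, Population defines one cohort for all objectives and states: "Patients who had positive troponin on postoperative day 4 will be excluded, since vital signs are only included up to postoperative day 3 for consistency". The Troponin row of the Data Dictionary repeats the rule ("Exclusion Criteria Patients who had positive troponin on postoperative day 4 will be excluded"). Neither place limits it to particular analyses.

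The main models stop earlier than the rule. Objective 1 is to "predict the daily maximum troponin level from postoperative days zero to two". Objective 2 is to "predict daily probability of MINS or death" over the same days. Primary Modeling aggregates vital signs and troponin by day. Data processing cuts the vital-sign series at the last troponin within 3 days (continuous outcome), or at the event, POD3, discharge or death (binary outcome).

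Duration of data collection runs from surgery "up to postoperative day 3 (since the MINS protocol monitors for 3 days) or hospital discharge or death, whichever occurs first". The Data Dictionary asks for "Preoperative and postoperative HS troponin values with time stamps" and gives no end date. Outcome counts only the first MINS event. The day windows under Data processing end at 96 hours after surgery. The expected cohort is given as "estimated sample size of 750, event rate of ~75".

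**The concern.** The stated reason is that vital signs are not available on POD4. That could justify not modelling an event on POD4. It does not justify deleting the same patient's POD0, 1 and 2 records, which are complete without POD4 vital signs.

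A prediction made on POD0, 1 or 2 would be made without knowing the POD4 troponin, and a user of the model could not apply the exclusion. The result also exists only for patients who stayed in hospital and were tested after the 3-day protocol had ended. The development cohort is therefore selected on later outcome and on later testing, and differs from the patients in whom the model would be used.

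The plan would not reveal this. Every fold of the repeated 5-fold cross-validation comes from the selected cohort, and nothing listed under Secondary, Sensitivity, and Exploratory Analyses brings these patients back.

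The rule is also hard to apply as written. It does not define a positive result, does not say whether it means the first positive or any positive, and gives no hours for POD4.

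**Working it through.** **Does the reason fit the models?** The outcome window is POD0–2 (Objectives; Duration of data collection; Primary Modeling). The predictors are daily summaries, with vital signs cut at POD3 at the latest (Data processing). No POD0–2 record uses a POD4 vital sign, so the reason does not reach these models.

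**Size if the rule means a first positive on POD4.** Inputs: 750 patients and about 75 events (Population), and 40%, 40% and 10% of MINS on POD0, 1 and 2 (Introduction). The 750 and 75 come without a derivation, so there is no formula to reproduce; their ratio is 75/750 = 10%. The POD0–2 share is 0.40 + 0.40 + 0.10 = 0.90, leaving 0.10 later.

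Assumptions: positive means MINS; early deaths are ignored (the plan expects them to be very rare); the counts are before this exclusion; and the whole later 10% is first positive on POD4. The last overstates the loss, because that 10% also contains POD3 events, which are kept. The plan does not say whether the 75 counts all MINS or only POD0–2 MINS, so both are shown.

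| | 75 = all MINS | 75 = POD0–2 MINS |
|---|---|---|
| All MINS | 75 | 75/0.90 = 83.3 |
| POD0–2 | 75 × 0.90 = 67.5 | 75 |
| Later, excluded | 7.5 (1.0% of 750) | 8.3 (1.1% of 750) |
| Patient-days lost, at most | 7.5 × 3 = 22.5 of 2,250 | 8.3 × 3 = 25 of 2,250 |
| POD0–2 rate, patients kept | 67.5/750 = 9.00% | 75/750 = 10.00% |
| POD0–2 rate, patients excluded | 67.5/742.5 = 9.09% | 75/741.7 = 10.11% |
| Shift, percentage points | +0.09 | +0.11 |

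If only half of the later events fall on POD4, the rates with exclusion are 67.5/746.25 = 9.05% and 75/745.8 = 10.06%, shifts of about 0.05 and 0.06 points.

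For scale, the standard error of a 10% rate in 750 patients is √(0.10 × 0.90/750) = 0.011, or 1.1 points. A shift of 0.11 is about a tenth of that.

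The 12–15% incidence in the Introduction, used instead of the plan's own count, gives 750 × 0.12 × 0.10 = 9.0 to 750 × 0.15 × 0.10 = 11.25 patients. The rates move from 10.80% to 81/741 = 10.93% (+0.13) and from 13.50% to 101.25/738.75 = 13.71% (+0.21).

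**Size if the rule means any positive on POD4.** Each POD0–2 event removed because troponin is still raised changes the rate to 74/749 = 9.88% (from 10.00%) or 66.5/749 = 8.88% (from 9.00%), a fall of about 0.12 points. The documents do not say how many such patients there are. Purely as assumed shares of 75 events, 10%, 25% and 50% still positive would leave 67.5/742.5 = 9.1%, 56.25/731.25 = 7.7% and 37.5/712.5 = 5.3%. These show sensitivity only and are not estimates.

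If positive means any raised troponin, chronic or nonischaemic elevations would add a further number that cannot be computed.

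**The case against.** **The effect is negligible.** Under the more natural first-positive reading the shift is about a tenth of one standard error. POD4 tests lie outside routine monitoring, so the true number may be smaller still. This stands, and it limits the importance of the point. The event rate also concerns the secondary outcome; no change in RMSE, AUC, R-squared or calibration has been shown. A reader might infer that the models' reported performance is materially biased, but the documents do not support that.

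**The rule removes true cases.** A reader might infer that it strips POD0–2 events with persistent elevation and so lowers the event rate materially. The literal wording permits this, but Outcome counts only the first event, which favours the narrower reading, and the documents give no number.

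**POD3 positives are kept, so the rule is uneven.** A reader might infer this too. It does not hold: vital signs are collected up to POD3, so treating POD3 and POD4 differently follows the stated reason, and adding POD3 information is a planned analysis.

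**One cohort for consistency.** Aim 3 of the machine-learning work compares it with the conventional models, and different cohorts would confuse that comparison. This stands and shapes the fix. Objective 5 also aims "to determine how many hours earlier than a binary MINS diagnosis were vital signs able" to predict it, and no POD0–2 limit is stated there. The rule may have some basis for that use, which this point does not cover.

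**Late detection.** A first positive on POD4 may reflect earlier injury that was missed, since the Introduction notes inconsistent monitoring. Keeping such patients as POD0–2 non-events may add slight label noise. This stands in part. The plan does not give it as a reason, and it has little force for the primary model, which uses observed daily troponin and has no non-event class. A sensitivity analysis can address it.

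**Conclusion.** The concern holds for the POD0–2 models: Objectives 1 and 2 and their variants under Objectives 3 and 4. The exclusion rests only on vital signs ending at POD3, these models use none from POD4, and the rule makes eligibility depend on a future result that exists only in some patients.

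Under the first-positive reading and the plan's own counts, the effect is small: at most about 7.5 to 8.3 of 750 patients and a rise of about 0.1 point in the POD0–2 event rate. This rests on positive meaning MINS and on the 40/40/10% split applying to this cohort. Under the any-positive reading the event rate would fall, by an amount the documents do not allow to be computed. The case for change is that the rule has no stated justification for these models and is cheap to remove, not that a large bias has been shown.

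**What to change.** - State that a positive troponin first seen after POD2, or persisting after POD2, is not a reason for exclusion from the POD0–2 models. Keep these patients with their observed POD0–2 troponin and MINS-or-death status.
- Leave the requirement of at least one postoperative troponin (Population; Missing data) unchanged.
- Report how many patients the present rule would remove, split into POD0–2 events and non-events, and refit with that exclusion as a sensitivity analysis. This also covers possible earlier undetected injury.
- Use the same patients in any head-to-head comparison of machine-learning and conventional models.
- If the rule is kept for the exploratory lead-time work, limit it to a first qualifying positive on POD4, and define a positive result and the hours of POD4.
- Reconcile the rule with Duration of data collection, which ends at POD3 although the rule needs a POD4 troponin.

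Cost: a few sentences of eligibility text, a few more charts to adjudicate, one extra model fit, and possibly slight label noise from late-detected injury.
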